6.6.5. Sensitivity Analyses for the Secondary Efficacy Analysis

6.6.5.1. Very Severe RSV LRTI

6.6.5.1.1. Analyses with Poisson Regression Model

A sensitivity analysis using a Poisson regression model with robust variance will be performed on All Randomized Set. The model will contain the following independent variables: the term of treatment group (ie, nirsevimab, no intervention), and age group at randomization (ie, age \leq 3.0 months, age $>$ 3.0 to \leq 6.0 months, age $>$ 6.0 months), and country (ie, France, Germany and United Kingdom) as covariates, adjusting for the log of the follow-up time as an offset. No interaction terms will be included in the model. The efficacy of nirsevimab in preventing very severe RSV LRTI, defined as $(1 \text{ minus the incidence rate ratio}) \times 100\%$. The incidence rate ratio and its corresponding 2-sided 95% CI will be estimated from the model by exponentiating the poisson model coefficients. Follow-up time for the log offset will be calculated as per Section 6.6.1. P-value will also be provided.

6.6.5.1.2. Tipping-Point Analysis

The same analysis as for the primary endpoint will be performed, imputing for all participants with missing data (ie who discontinued the study, or with a RSV test equals to missing or Not Done, or with missing oxygen saturation, or with missing oxygen supplementation) from both groups.

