8.1.2.3 Very severe RSV LRTI

A very severe RSV LRTI case is defined as:

- RSV LRTI hospitalization
- oxygen saturation < 90% (at any time during hospitalization)
- oxygen supplementation

With the addition of oxygen saturation < 90% and oxygen supplementation, very severe RSV LRTI cases are to be identified, described, and documented in the same way as RSV LRTI hospitalization (Section 8.1.2.2).

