9.4.3 Secondary Endpoints

9.4.3.1 Very severe RSV LRTI

If the efficacy of nirsevimab in preventing RSV LRTI hospitalization is demonstrated in the primary efficacy analysis, the very severe RSV LRTI through the RSV season will be compared between the nirsevimab and no intervention groups on all randomized participants using the same method for the primary efficacy analysis of the primary endpoint. The very severe RSV LRTI is a subset of RSV LRTI hospitalization with oxygen saturation < 90% (at any time during hospitalization) and oxygen supplementation. For participants with multiple very severe RSV LRTI episodes, only the first occurrence will be used in the analysis. If the lower bound of the 95% CI for the efficacy is > 0%, the superior efficacy of nirsevimab in preventing very severe RSV LRTI compared to the control group is demonstrated.

The above stated analysis on very severe RSV LRTI will be also conducted on the PPAS. The time to first very severe RSV LRTI will be analyzed using the Kaplan Meier curve and the Cox proportional hazard model, as described for the primary efficacy endpoint in Section 9.4.2, on all randomized participants.

Incidence of the very severe RSV LRTI will be summarized by the following subgroups:

- Age group at randomization: age \leq 3.0 months, age > 3.0 to \leq 6.0 months, age > 6.0 months
- Weight at randomization: weight $\leq 5 \text{ kg}$, weight $\geq 5 \text{ kg}$
- Gestational age: < 37 weeks, ≥ 37 weeks
- Gender: male, female
- Infants dosed in-season (dosed on or after the start date of the RSV season) and before the start of the RSV season.
- Country

Note: please refer to Section 4.2 for a definition of the start and the end of RSV season

Additional analyses if deemed necessary will be detailed in the SAP.

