6.6.2.2. Tipping-Point Analysis

Due to the open-label nature of the study, an excess of withdrawals might be observed in the no intervention group and be translated into a biased estimator when assuming the non-informative censoring hypothesis.

In order to test this hypothesis, a tipping point analysis^{8,9,10} will be performed to assess the impact of imputating missing data under a various range of hypotheses.

1. In order to perform the tipping point analysis, data will be imputed for all participants with missing data, (ie who discontinued the study, or with a RSV test equals to missing or Not Done) from both groups, several scenarios will be evaluated:
 - a. Best case scenario: no RSV LRTI hospitalization among the missing data in nirsevimab group whereas all missing data in the no intervention group will be imputed as RSV LRTI hospitalization.
 - b. Worst case scenario: all missing data in nirsevimab group will be imputed as RSV LRTI hospitalization whereas no missing data in the no intervention group will be imputed as RSV LRTI hospitalization.
 - c. The number of RSV LRTI hospitalizations imputed in each arm will be incremented from 0% (complete case analysis with no RSV LRTI hospitalization imputed in any arm), by 10%, to the total number of missing data in each arm. Remaining participants with missing data (from 90% of total number of missing data to 0%) will be then imputed as having no RSV LRTI hospitalizations.
2. For each combination:
 - a. Person-months will be imputed in both treatment groups using the overall distribution of person-months in the respective group for non-missing participants. The following values will be considered and evaluated as different scenarios: minimum value, Q1, Q2, Q3 and maximum value.
 - b. Corresponding Incidence Rates will be imputed in each treatment arm.
 - c. For non aggregated rows, Efficacy for participants with missing data will be provided

$$\text{Eff}_{\text{miss}} = 100 \times \left(1 - \frac{\text{Incidence Rate Miss Nirsevimab}}{\text{Incidence Rate Miss No Intervention}} \right) = 100 \times \left(1 - \frac{\text{IRN}_{\text{Miss}}}{\text{IRC}_{\text{Miss}}} \right)$$

- d. For non aggregated rows, Overall Efficacy will also be computed with its 2-sided 95% Confidence Interval (described by Breslow and Day as for primary analysis) and corresponding p-value

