6.6.7.4. Healthcare Utilization

For other exploratory endpoints listed below, tabular summaries overall and by country will be presented by treatment groups at the time of Primary Analysis through RSV season and at the time of First Year Analysis (through Day 151 and Day 181 post-dose/randomization). Categorical data will be summarized by the number and percentage of participants in each category. Continuous variables will be summarized by descriptive statistics (see Section 6.1 for details).

- LRTI hospitalization
- LRTI hospitalization outcome
- Duration of hospitalization (in case of partial or missing stop date, no duration will be calculated)
- Was PI the healthcare provider for this visit setting?
- Number of participants with RSV test Positive/ Negative/ Not done
- RSV Test Type
- Admission to the intensive care unit (ICU) and duration of stay (in case of partial or missing admission or discharge date, no duration will be calculated)
- Number of participants who require oxygen supplementation
- Number of participants in each category for oxygen supplementation
- Number of participants who require intravenous fluid administration

Duration of hospitalization (days) = Hospitalization Stop date – Hospitalization Start date + 1

Duration of ICU stay (days) = Discharge date – Admission date + 1

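### The tipping-point analysis for very severe RSV LRTI counts an infant as missing when any one component is missing, so admissions that a recorded component already excludes are put up for imputation

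*SAP*

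**What the plan says.** Protocol 9.4.3.1 and SAP 6.6.4.1 define the endpoint as a subset of admissions: "RSV LRTI hospitalization with oxygen saturation < 90% (at any time during hospitalization) and oxygen supplementation". Protocol 8.1.2.3 lists the same three requirements.

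SAP 6.6.5.1.2 sets out the tipping-point analysis in one sentence. It begins "The same analysis as for the primary endpoint will be performed, imputing for all participants with missing data". A bracketed list then says who has missing data: infants who discontinued, "or with a RSV test equals to missing or Not Done, or with missing oxygen saturation, or with missing oxygen supplementation". The items are joined by *or*, and both arms are included.

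The algorithm comes from SAP 6.6.2.2:
- In the worst case, "all missing data in nirsevimab group will be imputed as RSV LRTI hospitalization whereas no missing data in the no intervention group" is imputed as an event. The best case is the reverse.
- Between these, the imputed share rises from 0% "by 10%, to the total number of missing data in each arm".
- The person-months of infants in the pool are replaced by the minimum, a quartile or the maximum of the arm's distribution.

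The components are collected for LRTI admissions in general, not only RSV-positive ones (Protocol 1.3 footnotes and 8.7). A negative test is a recorded result, distinct from an untested admission: SAP 6.6.7.4 tabulates "Number of participants with RSV test Positive/ Negative/ Not done".

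**The concern.** The endpoint is a conjunction, but missingness is defined by a disjunction. Three kinds of admission have a known outcome (not very severe RSV LRTI) and still meet the SAP's definition of missing:

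- RSV test negative, with SpO2 or the oxygen field blank;
- RSV test not done, with lowest SpO2 recorded at 90% or above, or no oxygen given;
- RSV test positive and no oxygen given, with SpO2 blank.

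Neither 6.6.5.1.2 nor 6.6.2.2 exempts them. Such records are plausible, because testing follows hospital routine and data from outside hospitals are collected retrospectively (Protocol 8.1.2.2).

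SAP 3.2.6 names this analysis as a robustness check on the first key secondary estimand. If known non-cases are in the pool, the check partly varies outcomes that were observed. It can then report fragility in the worst case, or benefit in the best case, that the recorded data rule out.

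**Working it through.** **Inputs.** 14 430 infants per arm, a 0.4% control rate, 60% efficacy, 2-sided α of 5%, and at least 61 events for 90% power (Protocol 9.2, SAP 2.3). The method is the exact conditional binomial interval, with superiority if the lower 95% bound exceeds 0% (SAP 3.2.5).

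**The plan's own figure.** Under 60% efficacy and equal person-time, the probability that an event falls in the nirsevimab arm is 0.4/1.4. The exact test has 92.2% power at 61 events and 89.2% at 60. Among totals from 54 to 89, 61 is the first from which power stays at or above 90%, so the stated figure reproduces.

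**Planning splits.**
- Full sample: 14 430 × 0.004 = 57.7, about 58 control events; 57.7 × 0.4 = 23.1, about 23 nirsevimab events.
- At 61 events: 61/1.4 = 43.6, about 44; the other 17 are nirsevimab events.

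**Added nirsevimab events needed to tip (t).** No control events are imputed and person-time is held equal.

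| Control vs nirsevimab | Added | Lower 95% bound | p |
|---|---|---|---|
| 58 vs 23 | 0 | 34.7% | <0.001 |
| 58 vs 37 | 14 | +2.0% | 0.040 |
| 58 vs 38 | 15 | -0.3% | 0.052 |
| 44 vs 17 | 0 | 31.0% | 0.001 |
| 44 vs 26 | 9 | +1.9% | 0.041 |
| 44 vs 27 | 10 | -1.3% | 0.057 |

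So t = 15 for the full sample and t = 10 at 61 events.

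**Effect of the rule.** In the nirsevimab arm, let U be the infants whose outcome is truly undetermined and K the known non-cases counted as missing. The worst case adds U + K events as written and U when corrected. The tipping fraction is t/(U + K) as written and t/U when corrected. U and K are assumptions; 144 and 433 correspond to 1% and 3% of 14 430.

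Results at 58 vs 23, t = 15, K = 10:

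| U | Worst-case lower bound: written / corrected | Tipping fraction: written / corrected | First 10% step that tips: written / corrected |
|---|---|---|---|
| 10 | -11.9% / +11.3% | 75.0% / not reached | 80% / never |
| 15 | -23.4% / -0.3% | 60.0% / 100% | 60% / 100% |
| 30 | -57.9% / -35.0% | 37.5% / 50.0% | 40% / 50% |
| 60 | -126.6% / -103.7% | 21.4% / 25.0% | 30% / 30% |
| 144 | -318.0% / -295.2% | 9.7% / 10.4% | 10% / 20% |
| 433 | -974.7% / -952.0% | 3.4% / 3.5% | 10% / 10% |

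In the row U = 144, the grid moves a full step only because 10% of 144 rounds to 14, one short of t.

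At 44 vs 17, t = 10: with U = 5 and K = 5, the worst-case lower bound is -1.3% as written and +14.8% when corrected. With U = 10 and K = 10, the first step that tips is 50% as written and 100% when corrected.

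The reading reverses when t is above U but not above U + K. The plan would then report a tipping point that the recorded data exclude.

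**The case against.** This is a sensitivity analysis. Its stated motive (SAP 6.6.2.2) is excess withdrawal in the open-label control arm, and discontinued infants are in the same pool. If they dominate it, K hardly matters: with U = 144, the tipping fraction is 15/144 = 10.4% without known non-cases, 15/154 = 9.7% with 10 and 15/176 = 8.5% with 32. The protocol also asks for lowest saturation and oxygen use for every LRTI admission (8.7), so blanks may be few. All of this stands. It limits the size of the problem but does not make the rule right.

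Four stronger readings are not supported:

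- *The key secondary conclusion is at risk.* It rests on the exact test in SAP 6.6.4.1, which does not use this imputation.
- *Known non-cases drive the robustness result.* That needs the ratio of K to U, which the documents do not give. The 60% to 80% RSV share in Protocol 2.2 is for infant bronchiolitis, not LRTI admissions, so it cannot size the RSV-negative group, and no missing-field rate is stated.
- *Imputing equal percentages in both arms overturns the result.* It does pull efficacy toward zero. But adding 4 events to each arm (62 vs 27) leaves the lower bound at 30.5%, and adding 32 (90 vs 55) leaves it at 13.6%.
- *Never-admitted infants count as missing because they have no test.* This strains the text. The fields belong to the record of an LRTI admission.

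**Conclusion.** The point holds as a defect in a stated rule. SAP 6.6.5.1.2 places admissions with a known outcome in the imputation pool, which makes the best and worst cases too extreme and sets the tipping percentage too low whenever K is above zero. The count of added events needed to tip is unchanged at 15 (58 vs 23) or 10 (44 vs 17).

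The size depends on U and K, which have to be assumed. It runs from a reversed worst-case reading when few infants are truly undetermined (U = 10, K = 10) to a shift of 0.7 percentage points when discontinuations dominate (U = 144, K = 10). The figures assume equal person-time and the planning event split, and they ignore the SAP's replacement of person-months. Confidence is high that the rule is wrong as written; the effect in this trial cannot be judged from the documents. The change is worth making because it costs little.

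**What to change.** Replace the bracketed list in SAP 6.6.5.1.2 with a rule applied per LRTI admission within the analysis window:

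- An admission is undetermined only if at least one component is missing and no recorded component excludes the definition. That is, the RSV test is not Negative, lowest SpO2 is not recorded as 90% or above, and oxygen supplementation is not recorded as No.
- An infant is missing if any admission is undetermined and no very severe event has already been observed.
- Discontinuation before the end of the window without an observed event remains a separate route to missingness.
- All other infants stay observed, with their observed person-time.

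The rule has to work per admission. Applied per infant, one excluded admission would mark as a known non-case an infant who later discontinued or had a second, undetermined admission. The third item also settles a side effect of the present text, which read literally puts discontinued infants with an observed event into the pool.

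The cost is a short SAP edit and a few lines of programming, with no new data. SAP section 7 describes the Primary Analysis as already run, so the revised analysis should be labelled a later clarification and reported beside the one specified now. A count of U and K by arm would let readers judge how much the change matters.

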6.6.5.2. RSV LRTI Hospitalization in Each Country

6.6.5.2.1. Analyses with Poisson Regression Model

A sensitivity analysis using a Poisson regression model with robust variance will be performed on All Randomized Set. The model will contain the following independent variables: the term of treatment group (ie, nirsevimab, no intervention), and age group at randomization (ie, age \leq 3.0 months, age $>$ 3.0 to \leq 6.0 months, age $>$ 6.0 months) as covariates, adjusting for the log of the follow-up time as an offset. No interaction terms will be included in the model. The efficacy of nirsevimab in preventing RSV LRTI Hospitalization in each country, defined as $(1 \text{ minus the incidence rate ratio}) \times 100\%$ will be estimated from

the model by exponentiating the poisson model coefficients. Adjusted p-values based on Bonferroni-Holm procedure will be provided.

In addition, its corresponding adjusted 2-sided 95% CI based on Bonferroni-Holm procedure will also be provided at the time of First Year Analysis.

Follow-up time for the log offset will be calculated as per Section 6.6.1. See Section 6.6.4.2 for details about Bonferroni-Holm procedure. Only countries with adjusted p-values and the first country with non-significant adjusted p-value will be presented. Adjusted p-values will be computed using PROC MULTTEST in SAS.

6.6.5.2.2. Tipping-Point Analysis

The same analysis as for the primary endpoint will be performed using adjustment based on Bonferroni-Holm procedure (see 6.6.4.2 for details about Bonferroni-Holm procedure). Only countries with adjusted p-values and the first country with non-significant adjusted p-value from analysis in section 6.6.4.2 will be presented with same alpha level. Adjusted p-values will be computed using PROC MULTTEST in SAS.

6.6.6. Supplementary Analyses for the Secondary Efficacy Analysis

6.6.6.1. Very Severe RSV LRTI

6.6.6.1.1. Analyses with Per-Protocol Analysis Set

The - analysis of the secondary endpoint of very severe RSV LRTI described in Section 6.6.4.1 will also be conducted on the PPAS using adjustment based on Bonferroni-Holm procedure (see 6.6.4.2 for details about Bonferroni-Holm procedure). Only countries with adjusted p-values and the first country with non-significant adjusted p-value will be presented. Adjusted p-values will be computed using PROC MULTTEST in SAS.

6.6.6.1.2. Survival Analyses

A hazard ratio and the corresponding 2-sided 95% CI will be obtained from the Cox proportional hazard model with country (ie, France, Germany and United Kingdom) and age group at randomization (ie, age \leq 3.0 months, age $>$ 3.0 to \leq 6.0 months, age $>$ 6.0 months) as the covariates. The corresponding efficacy estimate is defined as (1 minus hazard ratio) \times 100%. A Kaplan-Meier curve for time to first very severe RSV LRTI will be generated based on the observed events and will include the adjusted p-value (based on Bonferroni-Holm procedure) from a log-rank test stratified by country and age group at randomization. Only

countries with adjusted p-values and the first country with non-significant adjusted p-value will be presented. Adjusted p-values will be computed using PROC MULTTEST in SAS. The algorithm for time-to-event calculation is the same as that for follow-up time as Section 6.6.1.

A log log plot to check Proportional Hazard assumption in the Cox proportional hazard model above will be provided.

Above analyses will be performed in the All Randomized Set.

6.6.6.2. RSV LRTI Hospitalization in Each Country

6.6.6.2.1. Analyses with Per-Protocol Analysis Set

The above-described analysis of the secondary endpoint of RSV LRTI Hospitalization in each country as described in Section 6.6.4.2 will also be conducted on the PPAS. Only countries with adjusted p-values and the first country with non-significant adjusted p-value will be presented. Adjusted p-values will be computed using PROC MULTTEST in SAS.

6.6.6.2.2. Survival Analyses

A hazard ratio will be obtained from the Cox proportional hazard model with age group at randomization (ie, age \leq 3.0 months, age $>$ 3.0 to \leq 6.0 months, age $>$ 6.0 months) as the covariates. The corresponding efficacy estimate is defined as $(1 \text{ minus hazard ratio}) \times 100\%$. A Kaplan-Meier curve for time to first RSV LRTI in each country will be generated based on the observed events and will include the adjusted p-values (based on Bonferroni-Holm procedure) from a log-rank test stratified by age group at randomization. At the time of First Year Analysis, the adjusted 2-sided 95% CI from the Cox proportional hazard model with age group at randomization (i.e., age \leq 3.0 months, age $>$ 3.0 to \leq 6.0 months, age $>$ 6.0 months) as the covariates will also be provided. The algorithm for time-to-event calculation is the same as that for follow-up time as Section 6.6.1.

A log-log plot to check Proportional Hazard assumption in the Cox proportional hazard model above will be provided.

Above analyses will be performed in the All Randomized Set.

Only countries with adjusted p-values and the first country with non-significant adjusted p-value will be presented. Adjusted p-values will be computed using PROC MULTTEST in SAS.

6.6.7. Exploratory Analysis

6.6.7.1. Very Severe RSV LRTI through Day 181 Post-Dosing/ Randomization

Efficacy and its 2-sided 95% CIs for nirsevimab in reducing the following efficacy endpoints as compared to the no intervention will be calculated using the exact method as described in the primary efficacy analysis for the following exploratory endpoint:

- Incidence of very severe RSV LRTI defined as RSV LRTI hospitalization with oxygen saturation < 90% (at any time during hospitalization) and oxygen supplementation, through Day 181 post-dosing/randomization (overall and in each country)

Analyses for Very severe RSV LRTI endpoint through Day 181 post-dosing/randomization will be performed only at the First Year Analysis after all data are collected. Participants who do not have Very severe RSV LRTI will be censored at the Day 181 or last available date for no event of interest whichever is earlier. For more details about these censoring rules, see section [6.6.4.3.4](#).

6.6.7.2. Survival Analyses of RSV LRT Hospitalization through Day 181 Post-Dosing/ Randomization

Same Cox proportional hazard model as in section [6.6.3.2](#) will be performed with country (ie, France, Germany and United Kingdom) and age group at randomization (ie, age \leq 3.0 months, age > 3.0 to \leq 6.0 months, age > 6.0 months) as the covariates.

For the analysis by country, only age group at randomization will be used as covariates as described in section [6.6.6.2.2](#).

In addition, Kaplan-Meier Plots will be provided for RSV LRTI hospitalization through Day 181 post-dosing/randomization (overall and in each country). P-value from Log Rank test will be provided.

6.6.7.3. Efficacy Analyses in the Subset of the Neonates and Infants Born in Season

Efficacy analysis of RSV LRTI hospitalization through the RSV season, through Day 151 post-dosing/randomization, and through Day 181 post-dosing/randomization will be also performed in the subset of the neonates and infants born in season (infants born in the season, ie, date of birth on or after the start date of RSV season).

Similar analyses as those for overall analyses will be performed (see sections [6.6.1](#), [6.6.4.3](#), [6.6.7](#)) and forest plots will be provided.

6.6.7.4. Healthcare Utilization

For other exploratory endpoints listed below, tabular summaries overall and by country will be presented by treatment groups at the time of Primary Analysis through RSV season and at the time of First Year Analysis (through Day 151 and Day 181 post-dose/randomization). Categorical data will be summarized by the number and percentage of participants in each category. Continuous variables will be summarized by descriptive statistics (see Section 6.1 for details).

- LRTI hospitalization
- LRTI hospitalization outcome
- Duration of hospitalization (in case of partial or missing stop date, no duration will be calculated)
- Was PI the healthcare provider for this visit setting?
- Number of participants with RSV test Positive/ Negative/ Not done
- RSV Test Type
- Admission to the intensive care unit (ICU) and duration of stay (in case of partial or missing admission or discharge date, no duration will be calculated)
- Number of participants who require oxygen supplementation
- Number of participants in each category for oxygen supplementation
- Number of participants who require intravenous fluid administration

Duration of hospitalization (days) = Hospitalization Stop date – Hospitalization Start date + 1

Duration of ICU stay (days) = Discharge date – Admission date + 1

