8.7 Medical Resource Utilization

For participants who report LRTI hospitalizations during the study, the investigator or designee will collect data about health care resource utilization associated with medical encounters.

For each case of LRTI hospitalization, the data collected in the eCRF should:

- Include the RSV test result, the lowest rate of oxygen saturation recorded, the duration of
 hospital stay, the list of medical interventions leading to end of the hospitalization (eg,
 oxygen supplementation, intravenous fluid administration, admission to intensive care
 unit), and outcome, and
- Exclude procedures, tests, and encounters mandated by the protocol.

The sponsor may use the collected data to conduct economic analyses.

Medical Resource Utilization will be evaluated in this study as an exploratory objective to investigate the effectiveness of nirsevimab compared with no preventive intervention in reducing utilization of key medical resources. Data on medical resource utilization will be collected either directly (if the attending physician is the Investigator) or retrospectively from the host hospital and/or the attending physician (if the attending physician is not the Investigator) to identify and measure the impact on these key medical resources arising from RSV LRTI hospitalization in infants.

The evaluation of resource use will be based on RSV LRTI hospitalizations and duration of stay, utilization of oxygen supplementation, administration of intravenous fluid, and ICU admissions and duration of stay.

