6.1. General Principles

All data processing, summarization and analyses will be performed using Fortrea's SAS Environment / Version 9.4 (or later) of the SAS® statistical software package.

The default summary statistics for quantitative variables will be the number of observations (n), mean, standard deviation (SD), median, minimum (min) and maximum (max), for those participants with data.

For qualitative variables, the number (n) and percentage (%) of participants with non-missing data per category will be the default summary presentation, and where appropriate and present, the number of missing values as a "Missing" category. Number of participants in the analysis population will be used as denominator for percentages calculation, unless otherwise stated in TFLs mock shell(s).

All statistical comparisons will be made using two sided tests at the $\alpha=0.05$ significance level unless specifically otherwise stated. All null hypotheses will be of no treatment difference. All alternative hypotheses will be two-sided.

Specifications for table, figure and data listing formats can be found in the TFL shells specifications for this study. Please refer to "2. General Format Guidelines" section within TFL shells for more details on presentation of results.

All analyses in the SAP will be carried out for all countries combined and as subgroup analyses by country.

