- ✓ For LRTI description, the rule “*If participants have multiple hospitalizations (respectively ICU stay) during the follow up period, duration of hospitalization (respectively ICU stay) will be the sum of each duration of hospitalization (respectively ICU stay)*” was finally not applied for Primary Analysis and will not be considered for First Year Analysis.

The following changes were performed for First Year Analysis:

- ✓ Incidence of hospitalizations for all-cause LRTI through Day 181 post-dosing/randomization will also be analysed by country
- ✓ Incidence of very severe RSV LRTI defined as RSV LRTI hospitalization with oxygen saturation < 90% (at any time during hospitalization) and oxygen supplementation, through Day 181 post-dosing/randomization will also be described by country

Tables for transparency will also be produced at the time of Second Year Analysis.

The Primary Analysis was re-run at the time of the First Year Analysis considering the same cut-off date and the same rules as the Primary Analysis.

An additional intercurrent event was added to consider participants who received Beyfortus as a routine medication during the study. They are excluded from the Per-Protocol Analysis Set and some analyses and listings are produced restricted to these specific participants (if at least 10 participants for tables / if at least one participant for listings).

8. Appendices

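### Length of hospital and ICU stay is summarised only among admitted infants, so these two endpoints are not a randomized comparison and do not measure the days that nirsevimab saves

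*SAP*

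**What the plan says.** Protocol 8.7 gives the exploratory aim as "to investigate the effectiveness of nirsevimab compared with no preventive intervention in reducing utilization of key medical resources". It bases the evaluation on RSV LRTI hospitalizations and their duration, oxygen supplementation, intravenous fluid, and ICU admissions and their duration.

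SAP 6.6.7.4 carries this out with tables by treatment group, through the RSV season at the Primary Analysis and through Day 151 and Day 181 at the First Year Analysis. The formula is "Duration of hospitalization (days) = Hospitalization Stop date – Hospitalization Start date + 1", with a matching one for ICU stay. For incomplete dates the entry reads "Duration of hospitalization (in case of partial or missing stop date, no duration will be calculated", and ICU stay has a parallel rule.

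For continuous variables the section points to SAP 6.1, which gives n, mean, SD, median, minimum and maximum "for those participants with data". For percentages SAP 6.1 says: "Number of participants in the analysis population will be used as denominator for percentages calculation, unless otherwise stated in TFLs mock shell(s".

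SAP section 7 reports that the rule adding up a participant's repeat hospital or ICU stays "was finally not applied for Primary Analysis and will not be considered for First Year Analysis". No replacement rule is given.

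**The concern.** A duration exists only where there was an admission. Nothing assigns zero days to an infant who was never admitted, and no total of days per randomized infant or per unit of follow-up is defined. The two duration rows therefore describe admitted infants only.

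Admission happens after randomization, and nirsevimab is expected to change it. The infants still admitted on nirsevimab need not resemble the admitted controls in severity. They may also differ in cause: SAP 6.6.7.4 lists LRTI hospitalization without the RSV qualifier of Protocol 8.7, so preventing RSV admissions raises the non-RSV share on nirsevimab. A difference in mean stay mixes any effect on the course of illness with a change in case mix, and leaves out the days saved because an admission did not happen.

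At stake is whether the two duration endpoints answer the question in Protocol 8.7, which also says that the sponsor may use the collected data for economic analyses.

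**Working it through.** **1. The plan's own figure.** Inputs from Protocol 9.2: 9620 infants per country (4810 per arm), 1.1% control incidence, 60% efficacy. Expected events = 4810 × 0.011 × (1 + 0.4) = 74.07, which matches the stated 74. The exact test conditional on 74 events, at 2-sided alpha 1.66%, has 91.4% power against the stated 90%. The incidence and efficacy inputs are therefore used below. The plan states no figure for utilization.

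**2. Days per randomized infant against mean stay.** Hospital days per 1000 randomized = 1000 × incidence × mean stay. The nirsevimab-to-control ratio of days is (1 − efficacy) × r, where r is the ratio of mean stays among admitted infants. The planned rows show only r. The documents give no length of stay, so means of 2, 4 and 6 days are assumed, with one stay per infant and r = 1:

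| Mean stay (assumed) | Control 1.1%: control vs nirsevimab | Control 0.86%: control vs nirsevimab |
|---|---|---|
| 2 days | 22 vs 8.8 | 17.2 vs 6.9 |
| 4 days | 44 vs 17.6 | 34.4 vs 13.8 |
| 6 days | 66 vs 26.4 | 51.6 vs 20.6 |

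Days fall by 60% in every row, while the difference in mean stay is zero.

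**3. Unequal mean stays.** At 60% efficacy, r = 1.25, 1.5 or 2 would look unfavourable to nirsevimab, yet the ratio of days is 0.50, 0.60 or 0.80, a fall of 50%, 40% or 20%. Days stop falling only at r = 2.5, since 0.4 × 2.5 = 1.

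**4. How case mix alone moves the mean.** Protocol 9.2 assumes 0.4% very severe within 1.1%, so about 36% of control admissions are very severe. Stays of 8 days (very severe) and 3 days (other) are assumed.
- Control, per 1000: 3.96 × 8 + 7.04 × 3 = 52.8 days over 11 admissions, mean 4.8.
- 60% efficacy on both types: 21.1 days over 4.4 admissions, mean 4.8. Days fall 60%.
- 50% on very severe and 65.6% on other: 1.98 × 8 + 2.42 × 3 = 23.1 days over 4.4 admissions, mean 5.25. Days fall 56%.
- 70% on very severe and 54.4% on other: 1.188 × 8 + 3.212 × 3 = 19.14 days over 4.4 admissions, mean 4.35. Days fall 64%.

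With stays of 6 and 2 days, and 42.5% and 70% efficacy on very severe and other cases, the mean rises from 3.45 to 4.09 days while days fall 53%. The mean can move either way with overall efficacy held at 60%.

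**5. Precision of the missing estimate.** With 14 430 per arm and 1.1% incidence, about 159 control and 63 nirsevimab infants are admitted. SE of the log ratio of days ≈ √[(1 + CV²)(1/63 + 1/159)], where CV is the coefficient of variation of stay (assumed). For a ratio of 0.40 the approximate 95% interval is 0.29 to 0.55 (CV 0.5), 0.27 to 0.60 (CV 1.0) or 0.24 to 0.68 (CV 1.5). At 0.86% incidence and CV 1.5 it is 0.22 to 0.72. The estimate would be informative at the planned size.

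**The case against.** A reader might infer that the whole utilization objective is analysed among hospitalized infants and cannot show a reduction. The documents do not support that. LRTI hospitalization, ICU admission, oxygen supplementation and intravenous fluid are counts of participants, with the analysis population as the default denominator, and these can show a reduction. Prevented admissions are also estimated with intervals over all randomized infants elsewhere in the SAP (6.6.1, 6.6.4.3, 6.6.9.1).

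Nor is a fall in hospital days impossible to see: the table gives n and mean by arm, so n × mean approximates total days. That stands, with limits. It is not specified and has no interval. Stays without a stop date drop out. With the summing rule withdrawn, it is unclear whether n counts infants or stays.

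The protocol lists durations rather than total days as endpoints, and promises only tabular summaries for them. SAP 6.6 makes exploratory analyses descriptive and untested. This limits the weight of the point. It does not make mean stay among admitted infants a measure of reduced use. That an economic analysis would be misled is conjecture, because it could draw on the individual stay data.

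The restriction to admitted infants is inferred from SAP 6.1 and the formula. SAP 6.6.7.4 does not name its population, and the table shells are not in the documents.

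Two cautions about a remedy also stand. Person-time built for a first event, which Protocol 9.4.2 ends at admission, cannot be the denominator for days that include repeat stays. And scoring early dropouts as zero days could bias the comparison against nirsevimab, because SAP 6.6.2.2 anticipates a possible excess of withdrawals in the no-intervention group.

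**Conclusion.** The point holds for the two duration endpoints and no further. As written, the between-arm difference in mean hospital or ICU stay is not a randomized comparison and does not measure days saved. Under the plan's rates it can show zero while hospital days per randomized infant fall by 60%. With unequal efficacy by severity, it can show a longer or a shorter stay on nirsevimab while days fall by 53% to 64%. These sizes rest on assumed lengths of stay, one stay per infant and the chosen efficacy splits. The identity that the ratio of days equals (1 − efficacy) × r needs only one stay per infant.

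Severity is minor: the analysis is exploratory, and no confirmatory conclusion depends on it.

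**What to change.** Add to SAP 6.6.7.4, or to the post-hoc section 6.6.9, an exploratory analysis labelled as added after the Primary Analysis:

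- For all randomized infants, with 0 for those not admitted, report total LRTI and RSV LRTI hospital days and ICU days by arm in each stated window.
- Express them per unit of observed follow-up and per 1000 randomized. Follow-up should continue past the first admission to the window end, last contact or routine Beyfortus, whichever is earliest. The first-event person-time of 6.6.1 should not be used. The follow-up-based rate reduces the effect of unequal dropout on the per-1000 figure, but still assumes that dropout is unrelated to later admission.
- Give the ratio between arms with a 95% interval from a bootstrap that resamples infants.
- Sum repeat stays within child, and report by arm the number of stays lost to missing dates.
- Keep stay among admitted infants, labelled as description that is not comparable between arms.
- Reconcile LRTI in SAP 6.6.7.4 with RSV LRTI in Protocol 8.7, and name the analysis set.

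Admission, discharge and ICU data are already collected, so no new data are needed. The cost is a modest amount of programming and an exploratory estimate added late to an open-label study.
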